12.9.5 Plasma Concentration

12.9.5.1 Continuous Summary

Descriptive summaries including geometric mean and SD, co-efficient of variation (%), geometric co-efficient of variation (%) of plasma concentrations will be presented by gender, time point and treatment groups. The summary will be based on PK analysis set.

All plasma concentration results will be listed by subject for PK analysis set.

In DDP: Table 14.5.1.1, Listing 16.2.10.2

12.9.5.2 Plasma Concentration Time Plots

Drug concentration profiles will be generated as follows:

- Mean Plasma concentration vs time will be presented for subjects within each treatment group along with error bars. Each group will be differentiated by color and symbol with appropriate legend. Y axis will be plasma concentration in ng/mL and X axis will be timepoints in hours. X axis will be displayed linearly proportionate to the actual timepoints.
- Log transformed plots will also be presented for the mean plots.

In DDP: Figures 14.5.1.2 and 14.5.1.3

12.9.6 Pharmacokinetic Parameters

The following PK parameters will be derived from plasma concentration using Phoenix WinNonLin software version 8.3 or higher for each measured analyte:

- Area under the plasma concentration-time curve from time of dosing (zero) to time t of the last measured concentration above the limit of quantification (AUC_{0-t})
- Area under the plasma concentration-time curve (AUC) from 0 to infinity ($AUC_{0-\infty}$)
- Elimination half-life ($t_{1/2}$)
- Observed maximum plasma concentration (C_{max})
- Time to observed maximum plasma concentration in plasma (T_{max})
- Elimination half-life ($t_{1/2}$)

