#### **4.3. Plasma Gelsolin**

Plasma gelsolin (pGSN) is a human protein produced and secreted by virtually every cell type, and it circulates at high levels in the blood of healthy individuals. At normal levels of 200-300 mg/L, it is the fourth most abundant protein in the circulation.

The therapeutic protein developed by BioAegis is rhu-pGSN and was formerly referred to as BG9385. It is identical to the complete natural protein and is comprised of 755 amino acids. The protein, like the natural protein, is non-glycosylated. The protein consists of six repeated domains, which make up three distinct actin binding sites, two that bind globular actin (G-actin) and one that binds filamentous actin (F-actin). Domain 1 plus the first 10 amino acids of domain 2 of gelsolin is the minimal fragment size required for its actin severing activity. Rhu-pGSN contains multiple calcium binding sites that regulate its activity. It is a highly conserved protein, as far back as drosophila.

Plasma gelsolin modulates inflammation while at the same time, boosting the body's ability to clear pathogens. It functions through mechanisms quite distinct from anti-inflammatory agents, which are antagonists of specific mediators or inhibitors of specific enzymes. Plasma gelsolin functions through a pleiotropic mechanism of action, scavenging toxic actin, binding inflammatory mediators and enhancing pathogen clearance. pGSN levels decrease markedly in a variety of clinical conditions such as acute respiratory distress syndrome, sepsis, major trauma, prolonged hyperoxia, malaria, and liver injury. The strength of the correlation between magnitude of decline in pGSN and likelihood of mortality is especially striking (Lee et al, 2006; 2008; 2009; Osborn et al, 2008). Specifically, a study of adult patients hospitalized with CAP showed that lower pGSN concentrations were significantly associated with more severe clinical outcomes (Self et al, 2018). Repletion of depressed plasma gelsolin levels with rhu-pGSN is expected to benefit patients through four distinct mechanisms that have been described in the literature:

1. Sequestration of released actin from sites of damage. This sequestration causes local depletion of pGSN while leaving large stores of pGSN continuing to circulate in healthy individuals. Modest reduction of systemic pGSN levels is then restored after healing is complete (Haddad et al, 1990; Lee et al, 1992).

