not be available at randomization or start of study treatment). Perform physical examination (PE) and document radiographic evidence of pneumonia (CXR or computed tomography ([CT] scan if CXR is inadequate) if not already completed within the previous 48 hours per SOC

6. Obtain blood and sputum cultures and electrocardiogram (EKG) per SOC (if not already performed). The microbiology lab is encouraged to perform sputum (bacterial, viral, and mycobacterial, as indicated) and blood cultures, sputum Gram-stains, antigen detection on respiratory and urine specimens, and RT-PCR diagnostic tests as possible.
7. Measure routine lab tests and biomarkers, including ferritin, D-dimer, C-reactive protein (CRP) and procalcitonin level at local laboratory; collect aliquots of blood for subsequent biomarker assays (likely to include, but not limited to IL1, IL6, IL10, tumor necrosis factor [TNF], etc.) for analysis at the central laboratory (see [Table 5](#) Schedule of Assessment and footnote '1' for details).
8. If eligibility criteria are satisfied, subject to be randomized (1:1 to treatment arms rhu-pGSN:placebo) within 12 hours of informed consent (Part 1) or within 24 hours of intubation (Part 2).

Randomized subjects will receive the assigned dose of rhu-pGSN or an equal volume of sterile saline placebo as soon as possible (ASAP), but beginning no later than 12 hours of randomization. The rhu-pGSN dose will be based on actual body weight given at 12 mg/kg. After reconstitution, rhu-pGSN should not be kept at room temperature for >2 hours prior to beginning the infusion. The initial dose of study drug (Dose #1) will be followed by dosing at 12 (Dose #2) and 36 hours (Dose #3) after the initial administration. Study drug is administered as a slow IV bolus at a rate of 20 mL/min through a 0.2 µm filter. The syringe, filter, and extension tubing for injection of study drug should be connected after disconnecting the IV as close to the subject as possible.

The primary efficacy endpoint will be assessed on Day 14, with secondary endpoints assessed on Days 7, 28, 60, and 90. Discharged subjects will undergo follow-up evaluation on Days 14, 28, 60, and 90.

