### **11.4.3. Pharmacokinetics and Immunogenicity**

To complete the PK analyses, plasma specimens will be periodically sampled relative to study drug administration and stored frozen for pGSN measurements. See [Table 5](#) and [Section 9.3](#) for collection time points. Plasma samples will be analyzed for  $C_{max}$ ,  $T_{max}$ ,  $T_{1/2}$ ,  $AUC_{0-8}$ ,  $AUC_{inf}$ .

Immunogenicity will be assessed on Day 1(predose), 28, and 90. Antibodies against rhu-pGSN will be assayed from frozen specimens to determine whether the investigational product induces an antibody response in recipients.

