12.9.6.1 Continuous Summary

Descriptive summaries including geometric mean and SD, co-efficient of variation (%), geometric co-efficient of variation (%) of PK parameters will be presented by gender and treatment group. The summary will be based on PK analysis set.

All PK parameters will be listed for PK analysis set.

In DDP: Table 14.5.1.6, Listing 16.2.10.3

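### SAP 12.9.6 derives PK parameters from plasma pGSN without handling the native protein; if the assay reads total pGSN, half-life and AUCinf are biased upward by a modest to several-fold amount

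*SAP*

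**What the plan says.** **Parameters.** SAP 12.9.6: "The following PK parameters will be derived from plasma concentration using Phoenix WinNonLin software version 8.3 or higher for each measured analyte". The list is AUC0-t, AUC0-inf, elimination half-life, Cmax and Tmax. No subtraction or model for native protein appears there or in SAP 12.9.5. SAP 11.7 and 11.7.1 define baseline and change from baseline in general terms, but neither PK section invokes them.

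**The analyte.** Protocol 4.3 says of the drug: "It is identical to the complete natural protein and is comprised of 755 amino acids". Of the native protein it says: "At normal levels of 200-300 mg/L, it is the fourth most abundant protein in the circulation". In severe illness, "pGSN levels decrease markedly in a variety of clinical conditions such as acute respiratory distress syndrome, sepsis"; no figure is given.

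**What is measured.** Protocol 11.4.3 says "plasma specimens will be periodically sampled relative to study drug administration and stored frozen for pGSN measurements". Protocol Table 5 puts pGSN levels and PK sampling in one row.

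**Samples.** Protocol 9.3 schedules a Dose #1 sample within 15 minutes before dosing and at 1, 2, 6 and 12 h after it. Dose #3 is sampled predose and up to 24 h after it.

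**Predose rule.** SAP 9.1 sets a predose concentration that is missing or below the quantification limit to 0.

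**Presentation.** SAP 12.9.6.1 says "PK parameters will be presented by gender and treatment group", based on the PK Analysis Set.

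**The concern.** The stated objective (Protocol 5.1.2) is the PK of administered rhu-pGSN. When the drug and a circulating protein are the same molecule, an assay for that molecule reads their sum. Three things follow if the sum is analysed as if it were drug:

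- The log-linear decline flattens toward the native level, so the half-life is too long.
- AUCinf extrapolates the native protein along with the drug.
- Cmax and AUC0-t include native protein too.

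The distortion varies with each subject's native level, so subjects' values are not comparable as drug parameters. The predose rule in SAP 9.1 suits a foreign drug. For a protein that is always present, a missing predose value is not zero, and subtracting zero would leave that subject uncorrected.

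**Working it through.** **The plan's own figure.** Protocol 4.4.2 reports that the median half-life in the earlier pneumonia study exceeded 17 h. It gives no concentrations and does not say whether the figure was baseline-corrected, so it cannot be reproduced.

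**Inputs from the documents.** Dose 12 mg/kg (Protocol 6.1); Dose #1 sampling times (Protocol 9.3); native level in health 200-300 mg/L (Protocol 4.3).

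**Assumptions.** Drug-only half-life 17 h; one compartment; negligible injection time; volume V of 45-80 mL/kg; constant native level B of 25-200 mg/L.

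**Formulas**
- k = ln 2 / 17 = 0.0408 per h
- initial rise R = 12 / V: 12/0.045 = 267 mg/L, 12/0.080 = 150 mg/L
- total concentration C(t) = B + R·exp(-kt)
- λ = minus the slope of ln C(t) fitted at 2, 6 and 12 h; apparent half-life = ln 2 / λ
- apparent AUCinf = 12B + (R/k)(1 - exp(-12k)) + C(12)/λ; drug-only AUCinf = R/k

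**Worked case, V = 45 mL/kg** (drug-only AUCinf 6,540 mg·h/L)
- B = 25: C = 270.8, 233.8, 188.5 mg/L; λ = 0.0362; half-life 19.1 h. AUCinf = 2,831 + 188.5/0.0362 ≈ 8,037; ratio 1.23.
- B = 200: C = 445.8, 408.8, 363.5 mg/L; λ = 0.0203; half-life 34.1 h. AUCinf ≈ 4,931 + 17,867 = 22,797; ratio 3.49.

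**All four corners**

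| Native level | Volume | Apparent half-life (drug-only 17 h) | AUCinf ratio | AUC0-12 ratio |
|---|---|---|---|---|
| 25 mg/L | 45 mL/kg | 19.1 h | 1.23 | 1.12 |
| 25 mg/L | 80 mL/kg | 20.8 h | 1.42 | 1.21 |
| 200 mg/L | 45 mL/kg | 34.1 h | 3.49 | 1.95 |
| 200 mg/L | 80 mL/kg | 47.3 h | 6.45 | 2.69 |

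The peak at time zero is inflated by (R + B)/R: 1.09-1.17 at 25 mg/L and 1.75-2.33 at 200 mg/L.

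**Dose #3.** With a wider volume range of 40-100 mL/kg and sampling to 24 h after Dose #3, the half-life ratio is 1.10-1.25 at 25 mg/L and 1.78-2.93 at 200 mg/L. The AUCinf ratio is 1.15-1.38 and 2.44-5.79. Drug-only half-lives of 10 and 24 h give the same direction.

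**Does subtraction repair it?** With a constant native level, subtracting the Dose #1 predose value returns 17.0 h and an AUCinf ratio of 1.00. Dose #3 needs the same Dose #1 value, because its own predose sample already contains drug.

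**Sensitivity to drift.** Let the native level be 100·(1 ± 0.2·t/12) mg/L, a 20% change over 12 h, and subtract 100:
- falling: corrected half-life 13.2 h (45 mL/kg) or 11.0 h (80 mL/kg); uncorrected 20.3 or 22.2 h
- rising: corrected 22.7 or 29.7 h; uncorrected 33.4 or 53.4 h

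With a falling level, the uncorrected value can be slightly nearer 17 h than the corrected one.

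**The case against.** **The assay is not described.** Total pGSN is an inference; laboratory detail is deferred to a manual outside these documents. The zero rule in SAP 9.1, and the heading of the SAP 12.9.5.2 plots as drug concentration profiles, could mean that another measure is intended. This stands as a reason to word the point conditionally. Protocol 11.4.3 and Table 5 still make pGSN the only measurement described.

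**The size is unknown.** A reader might infer that the reported half-life and AUCinf must come out far too large. The documents do not support that: levels fall in severe illness by an unstated amount, and at 25 mg/L the half-life bias is only 2-4 h. Nor is 17 h an established drug-only value; it may itself contain native protein.

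**Placebo.** A reader might infer that the SAP commits to a placebo half-life and AUCinf. Presentation by treatment group is the SAP's general convention (SAP 11.2). SAP 10.7 limits the PK set to subjects whose data give reliable estimates, which could remove flat native profiles. Placebo is not excluded by name, so one sentence is needed, but its tabulation is not established.

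**The predose sample is not strictly mandatory.** Protocol 6.1 requires the pGSN sample to be repeated if not taken within 15 minutes of the first dose, but Protocol 7.3 lets participants refuse some or all PK sampling.

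**Total levels have a use.** Protocol 4.3 aims at repletion, so total Cmax and AUC0-t are meaningful exposure measures. That supports keeping them, but not reporting their half-life or AUCinf as the drug's.

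**Consequences.** A reader might infer that these values will drive later dose-interval decisions. Neither document says so. The predose values are collected, so correction could also be done later without new data.

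**Subtraction is not neutral.** Protocol section 1 (Duration of treatment) says pGSN is consumed faster in severe illness, and Protocol 4.3 describes its restoration after healing, so the native level may move. This objection stands and shapes the fix.

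**Conclusion.** The point holds as a conditional one. The plan specifies no handling of native protein for an analyte that the protocol calls identical to it. If the assay reads total pGSN and the native level is roughly stable, half-life and AUCinf are biased upward, AUCinf more than half-life, and Cmax and AUC0-t also include native protein.

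Under the assumed inputs, the range runs from modest (half-life up by about 2-4 h, AUCinf 1.2-1.4 times at 25 mg/L) to several-fold for AUCinf at 200 mg/L (3.5-6.5 times, with half-life about 2.0-2.8 times). Native level, volume and drug-only half-life are all assumptions, so no single figure can be assigned to this trial. The primary efficacy analysis is untouched. The SAP should still be corrected, because as written it does not deliver the PK of the administered drug.

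**What to change.** Amend SAP 12.9.6 and 9.1:

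1. State what the PK assay measures.
2. For the rhu-pGSN arm, derive parameters from each concentration minus the subject's own Dose #1 predose value, for Dose #3 as well as Dose #1. Report uncorrected parameters alongside.
3. For this correction, treat a missing Dose #1 predose value as missing, not as 0.
4. State that half-life and AUCinf are not derived for placebo.
5. Use the placebo concentration profile to check drift in the native level, and interpret the corrected values accordingly.

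The cost is SAP wording and one derived variable; the samples are already scheduled. There are two downsides. Subjects without a predose sample drop out of the corrected parameters. Subtraction is also sensitive to drift, more so for Dose #3, whose last sample falls about 60 h after the first dose (36 + 24). That is why both sets of values should be shown.

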12.9.6.1 Continuous Summary

Descriptive summaries including geometric mean and SD, co-efficient of variation (%), geometric co-efficient of variation (%) of PK parameters will be presented by gender and treatment group. The summary will be based on PK analysis set.

All PK parameters will be listed for PK analysis set.

In DDP: Table 14.5.1.6, Listing 16.2.10.3

12.9.7 Immunogenicity

Number and percentage of subjects for presence of antibodies against rhu-pGSN will be summarized by treatment and visit. Percentages will be based on the FAS analysis set.

All Immunogenicity parameters will be listed for FAS analysis set.

In DDP: Table 14.6.1.1 and Listing 16.2.10.4

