#### **5.1.3. Immunogenicity Objective**

- To investigate the development of antibodies against pGSN post-treatment in rhu-pGSN vs placebo recipients compared to baseline

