## 11. STATISTICS

### 11.1. General Overview

All subjects given e 1 dose of study drug will be included in the Full Analysis Set (FAS) according to actual drug received; non-completers will be counted as failures in the primary efficacy analysis. Subjects receiving all 3 doses and evaluable for the primary Day 14 endpoint will constitute the per-protocol population for efficacy assessment. WHO severity score will be recorded daily while the subject is hospitalized, after discharge through Day 14, where feasible, and at each follow-up visit.

AE data will be summarized for the FAS by actual drug received using counts and proportions of subjects having an AE, each AE type, and an AE of each System Organ Class. SAEs and reasons for any early discontinuation will be summarized similarly. All deaths will be categorized by cause of death as per investigator assessment and relationship to study drug and/or COVID-19

Immunogenicity will be assessed on Days 1(predose), 28, and 90 days in all participants. Antibodies against pGSN will be assayed from frozen specimens to determine whether the investigational product induces an antibody response in recipients.

For Part 1, binary efficacy endpoints will be compared between treatments via stratified Cochran-Mantel-Haenszel (CMH) test and, to accommodate continuous covariates, via logistic regression. Continuous efficacy and biochemical endpoints will be compared between treatments via mixed model repeated measures analysis or analysis of covariance, depending on whether repeated measures are available or not. Time-to-event analysis via stratified log rank test and Cox proportional hazards model may also be carried out as supplemental analyses.

For Part 1, exploratory analyses looking at biomarkers and outcomes in each treatment arm will be conducted. Other exploratory analysis to compare the efficacy endpoint data from the rhu-pGSN group from this study to that of external control data may be carried out if appropriate. Sample size may be increased to improve the precision of the estimates of between-treatment comparisons if appropriate and if drug supplies are available.

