7.2.4 Immunogenicity

- *Presence of anti-pGSN antibodies on Days 1 (predose), 28, and 90*

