11.3.3 Visit Imputation

For assessments where shift summaries are required (WHO Severity Score and CURB-65 Score), records will be imputed for all subjects in Safety Analysis Set in all scheduled visits and marked as ‘Missing / Not Done’ if either the subjects did not attend the visit or discontinued or had missing assessment at the respective visit.

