11.7 Baseline

All analysis datasets having measurements taken at more than one visit/time point will have baseline flags. Baseline is defined as the latest non-missing measurement prior to IMP administration including repeat assessments and unscheduled visits. In case of multiple results at the same date/time, worst result will be considered as baseline in the following order or hierarchy: Abnormal CS, Abnormal NCS, Normal, Missing.

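### SAP 12.9.7 tabulates antibody presence by arm and visit, so no planned summary counts the subjects who became antibody-positive after treatment

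*SAP*

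**What the plan says.** The objective in Protocol 5.1.3, repeated in SAP 3.3, is "To investigate the development of antibodies against pGSN post-treatment in rhu-pGSN vs placebo recipients compared to baseline". Protocol 11.1 gives the purpose of the assay as "to determine whether the investigational product induces an antibody response in recipients", and Protocol 11.4.3 says the same.

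The endpoint is narrower. Protocol 5.2.2 and SAP 7.2.4 both define it as "Presence of anti-pGSN antibodies on Days 1 (predose), 28, and 90".

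The analysis in SAP 12.9.7 follows the endpoint: "Number and percentage of subjects for presence of antibodies against rhu-pGSN will be summarized by treatment and visit". It adds "Percentages will be based on the FAS analysis set" and "All Immunogenicity parameters will be listed for FAS analysis set". It does not define seroconversion, treatment-emergent antibody or boosted antibody, and it plans no between-arm estimate. The summary table in SAP 16.1 lists descriptive summaries only, and it names the PK analysis set where 12.9.7 names the FAS.

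**The concern.** The objective is about change within a person: was this subject negative before dosing and positive afterwards? The planned table answers a different question, namely what share of the arm is positive at each visit. In the Day 28 and Day 90 cells, a subject who was already positive before dosing counts the same as one who converted.

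If the table is the only summary, the study report would contain no pre-specified count of subjects in whom antibodies appeared after treatment. Any such count would be made from a listing, with the definition chosen after the results were visible. The question has some history: Protocol 4.7.1 mentions apparent anti-drug antibodies in some earlier recipients, although it adds that no harm was recognized.

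**Working it through.** The documents give no antibody rate, assay cut-point, titre rule or power for immunogenicity, so there is no stated figure to reproduce.

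**1. Does another SAP rule supply the missing comparison?**
- SAP 11.7: "All analysis datasets having measurements taken at more than one visit/time point will have baseline flags". This creates a flag, but 12.9.7 does not use it.
- SAP 11.7.1 defines change from baseline as a subtraction. It has no rule for a present/absent result.
- SAP 11.3.3: "For assessments where shift summaries are required (WHO Severity Score and CURB-65 Score), records will be imputed". Shift summaries are named for those two scores, not for antibodies.
- SAP 11.12 separates treatment-emergent from earlier events, but only for adverse events.

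None of them fills the gap.

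**2. What the by-visit counts identify when every sample is present.** Let N subjects be assayed at both visits, with a positive on Day 1, b positive on Day 28 and L losing positivity between them. Then

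new positives = b − a + L, which ranges from max(0, b − a) to min(b, N − a).

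N = 30 is the Part 1 arm size (Protocol 7.1); a and b are illustrative.

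| Day 1 | Day 28 | New positives possible | As % of 30 |
|---|---|---|---|
| 0 (0%) | 3 (10.0%) | exactly 3 | 10.0% |
| 5 (16.7%) | 8 (26.7%) | 3 to 8 | 10.0% to 26.7% |
| 6 (20.0%) | 6 (20.0%) | 0 to 6 | 0% to 20.0% |

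In the second row there are 30 − 5 = 25 Day 1 negatives, so the conversion rate among them could be 3/25 = 12.0% or 8/25 = 32.0%. The first row shows that the ambiguity disappears when nobody is positive on Day 1.

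**3. The same ambiguity from missing samples alone.** Assume 24 of the 30 have a Day 28 sample, 8 of them are positive, and nobody loses positivity. If k of the 5 Day 1 positives are among the 24, new positives = 8 − k. With k anywhere from 0 to 5, that is again 3 to 8.

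**4. Expected values.** Let q be the share positive on Day 1, s the induction rate among Day 1 negatives and r the share of Day 1 positives that lose positivity. All three are assumptions.
- Day 28 prevalence = q(1 − r) + (1 − q)s
- Net change from Day 1 = (1 − q)s − qr
- Treatment-emergent share of all subjects = (1 − q)s

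Example with q = 20%, s = 10%, r = 30%: prevalence = 0.14 + 0.08 = 22%; net change = 8% − 6% = 2%; treatment-emergent share = 8%.

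With s = 10%:

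| q | Prevalence, r = 0 | Net change, r = 0 | Prevalence, r = 30% | Net change, r = 30% | Treatment-emergent share |
|---|---|---|---|---|---|
| 0% | 10% | 10% | 10% | 10% | 10% |
| 10% | 19% | 9% | 16% | 6% | 9% |
| 20% | 28% | 8% | 22% | 2% | 8% |
| 30% | 37% | 7% | 28% | −2% | 7% |

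Without loss of positivity, and with all samples present, subtracting Day 1 gives the right answer. With loss it does not.

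**5. Fixed FAS denominator.** A subject with no sample cannot be in the numerator but stays in the denominator. If a share m is unsampled, independently of antibody status, a true prevalence of 20% is shown as 20% × (1 − m): 18% at m = 10%, 16% at m = 20% and 14% at m = 30%. For laboratory categories, by contrast, SAP 12.10.3.2 uses subjects with a result at the visit.

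**The case against.** The strongest reply is that baseline is not absent. Day 1 is one of the three tabulated visits, placebo is a column, and randomization gives both arms the same expected pre-existing reactivity. A reader can therefore see net change and compare arms. SAP 8.1 sorts listings by treatment, subject and date, so each subject's results appear together and converters in an arm of 30 can be counted by hand. The SAP also analyses exactly the endpoint that the protocol defines, so the gap between objective and endpoint begins in the protocol. The layout of Table 14.6.1.1 is in the Data Display Plan, which was not available and may contain more.

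All of this stands as a limit on the point. It does not remove it. Group-level net change is not the number of conversions (steps 2 to 4). The placebo arm balances Day 1 positivity only on average. With 30 per arm, the standard deviation of the chance difference is √(2q(1 − q)/30), which is 5.6, 7.7 and 10.3 percentage points for assumed q of 5%, 10% and 20%. Differences of that size could mask or mimic a modest induction rate, and 12.9.7 plans no between-arm estimate in any case. A hand count without a stated definition is weaker than a pre-specified one.

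**Conclusion.** The point holds in a limited form. The SAP text plans no within-subject comparison with Day 1, so no planned summary states how many subjects became antibody-positive after treatment, which is what the objective asks. The by-visit percentages can leave that number open over a wide range (3 to 8 in one example, 0 to 6 in another), and the FAS denominator lowers the later percentages when samples are missing.

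The size cannot be fixed from the documents. It depends on Day 1 positivity, loss of positivity and missing samples, none of which is given. At 0% on Day 1 there is no distortion from pre-existing reactivity; the denominator effect would remain.

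A reader might go further and infer that the table would roughly double the induced rate (19% shown against 10% induced, at 10% pre-existing), that the objective is not addressed at all, or that the trial cannot say who converted. The documents do not support this. Under the assumptions behind the 19%, subtracting the Day 1 row gives 19% − 10% = 9%, exactly the treatment-emergent share of 0.90 × 10%. The Day 1 row and the placebo column give group-level evidence, and the listing keeps the subject-level data. Nor do the documents present antibodies as a leading safety problem: Protocol 4.7.1 reports no recognized harm, and Protocol 4.4.2 reports no antibody formation in the inhaled healthy-volunteer study.

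**What to change.** Add to SAP 12.9.7:
- **Definition.** Treatment-emergent antibody means negative on Day 1 and positive on Day 28 or Day 90. If titres are reported, also define a boosted response as a pre-stated rise from a positive Day 1 result. State whether an early-termination sample counts as a later result, because SAP 11.3 presents that visit separately.
- **Summary.** Give the count, percentage and exact 95% CI by arm for conversion among Day 1 negatives with at least one later result. Report any boosted response separately among Day 1 positives.
- **Supportive table.** Keep the by-visit table and show the number sampled at each visit.
- **Analysis set.** Reconcile 12.9.7 (FAS) with 16.1 (PK analysis set).

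The cost is a few lines of SAP text, one or two derived flags and a few table rows, all from samples already scheduled. The objective already asks for this, so no protocol amendment is needed. SAP 9.4 provides the occasion: the blinded review meeting settles changes to planned analyses before database lock.
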